10.6.3. DSMB Responsibilities

The DSMB responsibilities will include:

- Reviewing the research protocol, informed consent documents and plans for data safety and monitoring;
- Recommending that participant recruitment be initiated after receipt of a satisfactory protocol:
- Evaluating the progress of the trial, including periodic assessments of data quality and timeliness, recruitment, accrual and retention, participant risk versus benefit, and other factors that can affect study outcome;

- Considering factors external to the study when relevant information becomes available, such as scientific or therapeutic developments that may have an impact on the safety of the participants or the ethics of the trial;
- Reviewing study performance, making recommendations and assisting in the resolution of problems reported by the PI;
- Protecting the safety of the study participants;
- Making recommendations to the PI concerning continuation, termination or other modifications of the trial based on the observed beneficial or adverse effects of the treatment under study; and
- Ensuring the confidentiality of the study data and the results of monitoring.

11: PSYCHIATRIC EMERGENCY PLAN

To detect suicidal ideation, the Outcome Assessor administers the Patient Health Questionnaire-9, which includes a question asking if the participant has thoughts that he/she would be better off dead or has had thoughts of hurting him/herself. If a participant endorses suicidal ideation, intent, or plan, staff is trained to follow a protocol. The protocol entails a specific determination of the suicidal risk and prescribes a set of actions.

For individuals who express suicidal ideation at any time during the study, staff will administer the Columbia Suicide Severity Rating Scale. Staff members are instructed that participants who have suicidal thoughts, or who express imminent intent with or without a method of self-harm, represent an immediate threat. Staff will contact [name], who will talk with the participant to assess the level of risk and determine an appropriate course of action. If the participant does not pose an immediate threat, staff will nevertheless notify [name], who will contact the participant within 24 hours to assess the participant and devise a plan of treatment.

All staff will be trained to implement the study Psychiatric Emergency Plan when indicated. The plan is as follows:

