If at any time severe depression is detected, or if a participant expresses thoughts of death or suicide, staff need to assess their risk for self-harm, and initiate the study Psychiatric Emergency Plan. Signs of severe depression include: poor hygiene or grooming, house in disarray (compared to previous times that the staff has interacted with the participant), weight loss, flat or sad affect, slowed speech, or statements of not wanting to live anymore. If severe depression is suspected, staff will say the following to the subject:

From what you're saying and from what I'm seeing, I suspect you are severely depressed and I'm concerned about this.

If the participant indicates (or you suspect) that they don't want to live anymore, you will need to do a suicide risk assessment by administering the Columbia Suicide Severity Rating Scale. When you are finished administering this scale, please go somewhere private (e.g., another room or your car) and call [name] ASAP. Have the participant's responses to the rating scale with you. Please do not leave the participant's home until you speak with [name]. He will provide guidance on how to handle the situation. He will likely ask to speak with the participant to further assess their risk of self-harm, and he will provide you with instructions for handling the situation immediately after he speaks with the participant.

If [name] determines that the participant is not suicidal, you can say "I'd like to know if you are receiving help for depression. Have you ever talked to a doctor or counselor or social worker about how you are feeling? Are you taking any medication for depression or nerves?" If the participant is currently being treated for depression, encourage them to keep up with the treatment and to let the treating physician know that their depression is not getting better.

If they are not being treated you can say: "It is not uncommon for people with diabetes to become depressed. In fact, it is a known complication of diabetes. But you don't have to feel this way. There

are many different kinds of safe and effective treatments for depression. Some people prefer to be treated with medications and other people decide to talk to a counselor.

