 - First, ask to see the participant's medications bottles (or a list of they use a med box), including supplements and over the counter drugs.
 - Second, ask the participant's if they take any other medications that they aren't showing you.
 - Enter the medication names, doses, and number of time per day that they take each medication into REDCap.
- 8) Patient Health Questionnaire (PHQ 9):
 - If the participant seems severely depressed, please email [name], [name], and [name] as soon as you can. If you think they are in a severe crisis, please follow the Psychiatric Emergency Plan.
 - If the participant responds with anything other than "0" for question 9, please administer the Columbia-Suicide Severity Rating Scale.
 - If the participant has suicidal ideation, please call [name] ASAP. Call [name] if you cannot reach [name].
 - If the participant does not have suicidal ideation, please email a description of the participant's responses to the PHQ and the Columbia to [name], [name], and [name].
 - Be sure to include your impressions/observations of the participant.
- 9) After completing an in-home assessment, the Outcome Assessor should not leave the participant's home until they check REDCap to verify that:
 - (1) The correct participant ID was selected.
 - (2) All questionnaires are completed.
 - (3) Missing data are properly coded.

Once the Outcome Assessor gets back to the office, they will enter in REDCap all data that were collected on paper forms (e.g., LAD, MOCA). The Outcome Assessor should also check to be sure that all hard copies are properly labeled with the date of the assessment, the participant's initials and ID, and the assessment type (e.g., 6 months). Assessments should be marked as "unverified". The Outcome Assessor will then email [name], [name], and [name] to inform them that the assessment was completed. The subject line of the email should contain the participant's initials and ID (for example, CRJC0001). The body of the email should contain the following completed table (note example provided). The image of the A1c readout should be attached to the email. The email must be sent within 1 business day of the completion of the assessment.

Notification of Completed Assessment Table

Participant ID:	CRJC00001
Assessment date:	9/14/18
Assessment:	Part 2 Baseline
Comments:	

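### For a participant who endorses PHQ-9 question 9 but is judged to have no suicidal ideation after the Columbia scale, Section 11 requires a call before staff leave and Appendix 4 asks only for an email

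*Combined protocol and SAP*

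**What the plan says.** **Section 11, Psychiatric Emergency Plan.** The section names the PHQ-9 as its means of detecting suicidal ideation and describes the relevant item as "a question asking if the participant has thoughts that he/she would be better off dead or has had thoughts of hurting him/herself". The Plan opens broadly: "if a participant expresses thoughts of death or suicide, staff need to assess their risk for self-harm, and initiate the study Psychiatric Emergency Plan". The Columbia scale has its own trigger: "If the participant indicates (or you suspect) that they don't want to live anymore, you will need to do a suicide risk assessment". After the scale, staff are told "please go somewhere private (e.g., another room or your car) and call" the clinician at once, and then "Please do not leave the participant's home until you speak with" him. It is the clinician who then determines whether the participant is suicidal. A written report by email follows when staff are back at the office.

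**Section 11 introduction and Section 10.3.1.** If there is no immediate threat (or risk), staff still notify the clinician, "who will contact the participant within 24 hours to assess the participant and devise a plan of treatment" in the wording of Section 11. Neither place says by which channel the clinician is notified.

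**Appendix 4 item 8, instructions for the Outcome Assessor.** Any answer to question 9 other than zero leads to the Columbia scale. The instruction then divides. With suicidal ideation, the assessor calls as soon as possible, and a second contact is named. Without it: "If the participant does not have suicidal ideation, please email a description of the participant's responses to the PHQ and the Columbia" to three named recipients. The Psychiatric Emergency Plan is invoked only if the assessor thinks the participant is in a severe crisis.

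**Appendix 3 item 8, instructions for all staff.** Suicidal ideation leads to a call, with a back-up contact. The Plan is again tied to a severe crisis.

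**The concern.** Section 11 and Appendix 4 both govern what the assessor does in the home after the Columbia scale. If they differ for the same participant, two trained assessors can each follow current text and act differently: one speaks to the clinician before leaving, the other sends an email for which item 8 gives no deadline.

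The instructions also place the judgement with different people. Under Section 11 the clinician decides after the call. Under Appendix 4 the assessor's own finding of no ideation decides whether a call is made at all.

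At stake is consistent handling of a participant-safety step at in-home assessments. The primary analysis is not affected.

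**Working it through.** No stated figure has to be reproduced. The check sets the passages side by side, then bounds the number of visits.

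**Step 1: does an endorsed question 9 fall under Section 11?** The Columbia trigger in Section 11 (not wanting to live) is not worded identically to any non-zero answer. But Section 11 names this PHQ-9 item as its detection tool, and its Plan starts for any expressed thoughts of death or suicide. Section 6.2 (Depression) calls it the question on suicidal ideation and requires the Columbia scale for any positive answer. An endorsed item is therefore within the Plan's opening trigger.

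**Step 2: compare the instructions after the Columbia scale.**

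| After a non-zero question 9 | Section 11 | Appendix 4 item 8 |
|---|---|---|
| Ideation found | Call; remain until the clinician has been spoken to | Call, with back-up contact; no stay rule |
| No ideation found | Call; remain until the clinician has been spoken to | Email; no call, no stay rule |

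In the first row both require a call and only the stay rule differs. In the second row the channel and the timing both conflict.

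**Step 3: does Appendix 4 import Section 11 by reference?** Only for a perceived severe crisis. An assessor who has just concluded that there is no ideation would not ordinarily take that route.

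**Step 4: does the 24-hour rule settle it?** No. Notification without a stated channel could be met by a call or an email, and the clinician's contact within 24 hours can follow either. Appendix 4 does not mention that contact. Because names are removed, the text does not show whether the clinician is among the email recipients.

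**Step 5: how many visits?** Table 5 schedules the PHQ-9 at baseline and at the follow-ups, which are at 6 and 12 months: 3 occasions. Section 5.1 gives 156 randomized participants.

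- Maximum administrations in randomized participants: 3 x 156 = 468, with no attrition or missed visits.
- The documents give no endorsement rate. If 3% to 10% endorsed question 9 (an assumption): 0.03 x 468 = 14.0 and 0.10 x 468 = 46.8, or about 14 to 47 visits. That range counts all endorsers.
- The call-versus-email conflict reaches only endorsers then judged to have no ideation. The documents give no basis for that fraction.

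**The case against.** The best defence is that the two texts are tiered: Appendix 4 describes a broad screen, and Section 11 the full response for someone who does not want to live. Training supports this to a degree. Section 7.9 sets a low threshold for alerting the clinician, Section 11 says all staff are trained on the Plan, and Appendices 3 and 4 point to it in a crisis. The difference in triggers is real and narrows the point. It does not remove it, because the Plan's opening trigger takes in any expressed thoughts of death or suicide and Section 11 relies on this very PHQ-9 item.

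It might also be said that the Appendix 4 email is simply the report that Section 11 requests later. But in Section 11 the report follows the call, whereas in Appendix 4 the call and the email are alternatives, chosen by whether ideation is found.

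A reader might infer several stronger things that the documents do not support:

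- **That the assessor may email instead of calling whenever question 9 is endorsed.** With ideation present, Appendix 4 requires a call.
- **That Section 11 contradicts itself by allowing the call from the car.** Read in context, staff step out for privacy and the visit is not over; the clinician is expected to ask to speak with the participant.
- **That staff have no second person to call.** Section 11 is silent, but Appendices 3 and 4 name one for suicidal ideation.
- **That the 24-hour contact is a third, incompatible rule.** It can sit alongside either a call or an email.
- **That 14 to 47 visits are affected.** That range is for all endorsers under an assumed rate, not for the affected subset.

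**Conclusion.** The point holds in a confined form. For a participant with a non-zero question 9 and no suicidal ideation after the Columbia scale, the current text of Section 11 requires a conversation with the clinician before staff leave, and the current text of Appendix 4 requires only an email. Where ideation is present, the remaining difference is that the stay rule appears in Section 11 alone. The 24-hour clinician contact in Sections 10.3.1 and 11 is missing from Appendix 4, which is a gap rather than a contradiction.

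The size is not known: some subset of question-9 endorsements among at most 468 planned administrations in randomized participants. The conclusion rests on reading an endorsed question 9 as within the Plan's opening trigger, which Section 11's own description of the item supports. It does not depend on any assumed endorsement rate, since a single such visit meets both instructions. The passages should be reconciled; no view is taken here on which rule is right.

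**What to change.** Reconcile Section 10.3.1, Section 11, Appendix 3 item 8 and Appendix 4 item 8 into one instruction, and use the same text in Section 11 and Appendix 4. For each Columbia result it should state:

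- whether staff must speak to the clinician before leaving the home;
- by which channel the clinician is informed;
- when the clinician contacts the participant.

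Carry the back-up contact in Appendices 3 and 4 into Section 11. The responsible clinicians decide which rule applies to each result.

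The cost is a wording change in the manual and a note to trained staff. If the visits are already complete, the sponsor can still record which instruction was followed.

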12.1. General issues

All assessment forms will be created in REDCap, and all data files will be housed on the study server, which is secure and encrypted. The ED staff and the Outcome Assessor will use a laptop to administer all assessments. The computer will prompt staff to ask each question and enter the participant's response directly into the computer. Staff will have hard copies of the assessment available at all times should the computer malfunction.

Prior to each assessment, staff will prepare an assessment folder. The folder will contain all necessary forms and instructions (e.g., Informed Consent documents, receipts for dispensing incentives, worksheets for the neuropsychological test), money for incentives, and the educational materials.

All assessments will be audio recorded. All computers used for data collection and storage will be encrypted and password protected. The following data will be collected via hardcopies, which will be entered by hand by staff into REDCap: (1) intervention notes; (2) intervention forms; and (3) HbA1c results.

Data management and cleaning will be ongoing throughout the study. Inconsistencies and missing data will be reconciled (e.g. call participant or check EMR for missing data). There will be separate database for each time wave. Study identifiers will be used to link data from multiple time points for longitudinal analyses. On a monthly basis, the Project Director will run frequency distributions for all variables to check for accuracy.

Although there will be efforts to minimize missing data, missing data will be handled in the following way: at each time point, participants who complete that assessment will be compared to those lost to attrition on all baseline variables as well as those from previous time points if appropriate. Any variable(s) that emerge as significantly different will be controlled statistically.

12.2. Description of computing environment

12.2.1. Hardware

Computers will be purchased for project staff, and they will be password protected and encrypted. All computers will be serviced by the Information Technology (IT) department at Thomas Jefferson University.

12.2.2. Software

All data will be managed and analyzed with SAS, SPSS, or Mplus, TreeAge Pro, and Excel. REDCap will be used to create all data forms.

12.3. Participant identification and confidentiality

Study identifiers will be used on all data forms except when absolutely necessary (e.g. Community Health Worker Encounter Form). Neither participant names, nor any other identifying information other than the unique identifiers, will ever be on the data forms. All hard copies of participant information (e.g., signed informed consent forms) will be stored in locked file cabinets stored in the PI's lab. Each participant will have 2 charts: an identified chart and a de-identified chart, and each will be stored in separate file cabinets in the PI's lab. The following will be stored in the identified chart: the participant's contact information, the signed consent form, and any other documentation that contains identifying information (e.g., documents uploaded to EMR that require identifying information). The following will be stored in the de-identified chart: all hard copies of assessment forms, intervention forms, de-identified treatment notes, and administrative forms. None of the documents contained in the de-identified chart will have the participant's name. A master list linking participants' names with their study identifiers will be stored in an encrypted password protected file on the study server, and will be restricted to specific staff.

12.4. Procedures for Data Checking and Editing

After completing an in-home assessment, the Outcome Assessor should not leave the participant's home until they check REDCap to verify that: (1) that the correct participant ID was selected; (2) all questionnaires are completed; and (3) missing data are properly coded. Once the Outcome Assessor gets back to the office, she will enter in REDCap all data that were collected on paper forms (e.g., LAD, MOCA). The Outcome Assessor should also check to be sure that all hard copies are properly labeled with the date of the assessment, the participant's initials and ID, and the assessment type (e.g., 6 months). Assessments should be marked as "unverified". The assessor will then email the Project Director and the Study Coordinator to inform them that the assessment was completed. The subject line of the email should contain the participant's initials and ID (for example, CRJC0001). The body of the email should contain the following completed table (note example provided). The image of the A1c readout should be attached to the email. The email must be sent the same day that the assessment occurred.

Notification of Completed Assessment Table

Participant ID:	CRJC00001
Assessment date:	9/14/18
Assessment:	Part 2 Baseline
Comments:	

Once the email has been sent, the Outcome Assessor should upload the recording of the assessment to the designated location on the shared drive. All tapes must be uploaded and all hard copies of paperwork must be turned into the Study Coordinator within 1 business day of the assessment. Staff will scan all hard copies and store them on the appropriate location of the shared drive. Staff will download the A1c image and store it in the appropriate location on the shared drive.

The Research Assistant, who is employed by the Department of Neurology at Jefferson and is not paid by this grant, will then review the tape and update the REDCap files as necessary. All data edits made by the Research Assistant must be recorded on the Assessment Check excel file, which will be stored on the shared drive. If additional information is required from the Outcome Assessor (for example, a skipped question), the Research Assistant will email the Outcome Assessor, the Project Director, and the Study Coordinator. The subject line should be the participant's initials and ID. The body of the email should include the following table:

Data Query Table

Participant ID:	CRJC00001
Assessment date:	9/14/18
Assessment:	Part 2 Baseline
Data issue:	PHQ6 is blank and is not asked on the tape

Within 1 business day of receiving this email, the Outcome Assessor should "reply all" with the response to the query. The Research Assistant will then update REDCap as necessary, and will indicate in the Assessment Check excel file that the Outcome Assessor responded to the query. Once all queries have been resolved, the Research Assistant will mark the assessment as "verified" in REDCap.

Data forms (both hard and electronic forms) will be reviewed within 1 week of completion by the Research Assistant. This review is performed to check that all information is accurate, check marks or circled answers are clearly demarcated (if completed on a hard copy), and that each item is completed. The Research Assistant will also check to assure that consent forms are signed appropriately. The Research Assistant will then scan the consent form and store it on the server. The hard copy will be stored in the participant's research chart.

All assessments will be audiotaped using a digital audio recorder. This is explained to participants in the consent form. The recorder is not turned on until after the consent form has been signed by the participant and the person conducting the consent interview. Staff will be instructed to refrain from mentioning any identifying information (e.g., the participant's name) during the recording. Staff will begin each recording by stating the participant's unique identifier, the date, the time, and assessment type. For example, "My name is XXXX. Today is 9/1/17, 10:00 AM, and I am with CBWR00001 to conduct the Part 2 of the baseline assessment". Within 1 week of an assessment being completed, the Research Assistant will listen to the audio recording of the assessment, and compare it to the corresponding data entered into REDCap.

Data quality is maintained through a variety of analyses that target anomalies, delinquent data, and key-entry errors. A part of this process is to analyze the frequency of errors according to type to determine if certain types of errors are recurrent. Modifications to the data forms are made if the same types of errors occur frequently. If the PI deems necessary, steps are taken to resolve the problems by providing additional training for staff and/or modifying the study forms. In addition, random audits of the data collected on the forms may be performed by the Project Director by checking for accuracy and completeness.

